6.3.1 ORR

ORR is defined as the complete response (CR) rate + partial response (PR) rate. A patient's best response after the start of study treatment will be used for this determination, as assessed by independent, blinded, central review as per RECIST guideline version 1.1 (Eisenhauer, 2009).

In order to define the best overall response, the following rules will be applied:

- CR and PR need to be confirmed no less than 4 weeks apart
- If SD or NON-CR/NON-PD is before 6 weeks after start of study treatment the SD, NON-CR/NON-PD is not taken into account and put to NE in the determination of best overall response.
- Best overall response is defined as the best response after start of study treatment in the following order of assessments: CR, PR (both need to be confirmed), SD or NON-CR/NON-PD (if not too early), PD, NE. For PD there is no confirmation needed.

Among patients in the ITT population, the overall frequency of responders, i.e., patients whose best response after the start of study treatment is CR or PR, will be compared between treatment arms using the Cochran-Mantel-Haenszel (CMH) test, stratified by performance status grade and tumor location.

Subjects who did not receive any study treatment, or who do not have a valid post-treatment efficacy assessment will be classified as not evaluable (NE) or non-responders for response classifications. These subjects will be included in the denominator of the ITT analysis for calculation of response rates.

In SAS, this will be performed with PROC FREQ specifying the cmh option in the table statement. Performance status grade and tumor location, both assessed at baseline, will be included as stratification factors (i.e., controlling for these variables in the table statement); if necessary, a single four-level categorical variable will be derived whose values represent the four distinct patterns of performance status and tumor location.

The significance of the asymptotically estimated CMH statistic will be determined using a re-randomization procedure. The Odds Ratio (OR and confidence limits from the asymptotic test, will be reported.

The Breslow-Day test should be inspected to confirm that there is no evidence of interaction between the stratification factors and treatment. Evidence of heterogeneity in one or both of the strata does not invalidate a significant treatment effect; in such a case, the finding should be reported in a separate table in which the OR and confidence limits of the treatment effect in each level of the strata should be presented.

Refer to the table below for a description of the primary and sensitivity analyses that will be performed. These will be reported only during the final analysis. Breslow-Day statistics do not need to be reported.

No.	Stratified	Re-Randomized	Endpoint Review	Population
1. Primary	Yes	Yes	Central	ITT
1. Sensitivity	Yes	No	Central	ITT
2. Sensitivity	Yes	Yes	Central	PP
3. Sensitivity	No	No	Central	PP

Confidential

6.3.2 DOR

Duration of response is defined as the time from the date of first documented response until date of documented progression or death in the absence of disease progression (i.e. date of PFS event or censoring – date of first response + 1). The end of response should coincide with the date of progression or death from any cause used for the PFS endpoint. The time of the initial response will be defined as the first date of the dates contributing towards the first visit response of PR or CR. If a patient does not progress following a response, then their DoR will use the PFS censoring time. DoR will not be defined for those patients who do not have documented response.

To assess for DOR differences between treatment arms, the Cox PH model will be used, specifying the Efron method for ties. This will be done using `PROC PHREG` in SAS, in which performance status and tumor location will be added in a separate `strata` statement.

The significance of the asymptotically estimated statistics will be determined using a re-randomization procedure. The hazard ratio, and confidence limits from the asymptotic test, will be reported.

The Kaplan-Meier estimator, and their respective confidence limits, will all be displayed in a table. To confirm proportionality of the hazards, the log-log survival plot should be inspected, using `PROC LIFETEST` and, at a minimum, specifying treatment arm in the `strata` statement (the stratification variables may also be included); these plots will not be included in the set of outputs.

Supplementing this test will be a Kaplan-Meier plot showing DOR duration, in months, by treatment arm. Underneath the plot should be a table displaying the number at risk by treatment arm at 0.5-month intervals. The plot should contain an inset with the hazard ratio, the corresponding confidence limits.

A log rank test will be performed as a sensitivity analysis.

6.3.3 Safety Analyses

The assessment of safety will be based mainly on the frequency of adverse events based on the Cancer Therapy Evaluation Program (CTEP) Active Version of the NCI Common Terminology Criteria for Adverse Events (CTCAE 4.0) grade. The CTEP Active Version of the CTCAE is identified and located on the [CTEP website](#). If the severity or intensity is not specifically graded by the guidance document from CTEP, the site investigators have been instructed in the protocol to revert to the general definitions of grade 1 through grade 5 shown in the table below. Additional information about adverse event or unanticipated problem reporting can be found in the protocol, section 8.

Severity	Description
Grade 1	Mild; events require minimal or no treatment and do not interfere with the participant's daily activities.
Grade 2	Moderate; events result in a low level of inconvenience or concern with the therapeutic measures. Moderate events may cause some interference with functioning.
Grade 3	Severe; events interrupt a participant's usual daily activity and may require systemic drug therapy or other treatment.
Grade 4	Life threatening or disabling; patient at risk of death at the time of the event.

Confidential

Grade 5	Death related to AE.
---------	----------------------

The following tabular summaries of adverse events will be provided using the safety population:

- All AEs by SOC and CTCAE term, by treatment arm and overall
- Patients with at least one AE by SOC and CTCAE term, by treatment arm and overall
- Patients with at least one AE by relatedness, by treatment arm and overall
- Patients with at least one AE by severity, by treatment arm and overall
- All serious AEs (SAEs) by SOC and CTCAE term, by treatment arm and overall
- Patients with at least one SAE by SOC and CTCAE term, by treatment arm and overall
- Patients with at least one AE that led to a change in study medication (e.g., dose modification, interruption, or permanent discontinuation), by treatment arm and overall
- Patients with at least one AE requiring a change in concomitant therapy (e.g., addition, interruption, discontinuation, or change in a concomitant medication, therapy, or treatment), by treatment arm and overall.

Adverse events that are still ongoing at the time of data cut-off should not be included in any of the tables described above. Instead, a separate table should be presented containing all on-going AEs by SOC and CTCAE term, by treatment arm and overall.

All SAEs which are possibly related or unexpected are required to be reported to sponsor or sponsor designated vendor using a serious adverse event report form. The SAE β - data, or other important documents.

The number of death cases and cause of death will be summarized separately using the ITT population, by treatment arm and overall. A listing will be provided containing patient ID, site ID, age, sex, treatment arm (if applicable), relatedness to study drug (if applicable), randomization date, treatment start date (if applicable), date of death, and site-reported narrative for all patients who die during the study.

6.3.4 z,

These analyses fall outside of the scope of this SAP, please refer to the separate PK Analysis Plan managed by the PK analysis vendor.

6.3.5 $z\beta$ /

These analyses fall outside of the scope of this SAP, please refer to the separate PRO Analysis Plan managed by the PRO analysis vendor.

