5.3.1. Discontinuation of Treatment

The Investigator must protect the subject's welfare and may discontinue any study treatment at any time when this action appears to be in the subject's best interest. The reason for the subject's discontinuation must be recorded in the subject's electronic case report. Possible reasons for the discontinuation may include, but are not limited to, the following:

- Disease Progression defined as follow: disease progression documented by CT scan (or MRI) based on RECIST version 1.1 criteria, as determined in the protocol;
- Adverse Event;
- Any significant Protocol Violation as per protocol;
- Withdrawal of consent by an enrolled subject.

5.3.1.1 Patients requiring delay for more than 3 weeks because of toxicity.

- 5.3.1.2 Unacceptable toxicity from FFX or mFFX + devimistat (Grade 3 or more severity of toxicity).
- 5.3.1.3 The subject becomes pregnant (treatment should be discontinued immediately)
Intercurrent illness with a condition, injury, or disease unrelated to the intended disease for which the study is investigating, that renders continuing the treatment unsafe or regular follow-up impossible.
- 5.3.1.4 General or specific changes in the patient's condition that in the opinion of the treating physician renders the patient ineligible for further investigational treatment.
- 5.3.1.5 Recurrent grade 4 adverse events despite all appropriate dose reductions.
- 5.3.1.6 Non-compliance with investigational treatment, protocol-required evaluations or follow-up visits.
- 5.3.1.7 Other reasons as determined by the Investigator or Sponsor: A subject may have study treatment discontinued if, in the opinion of the Investigator or Sponsor, it is not in the subject's best interest to continue; Unambiguous clinical progression documented by the Investigator in the absence of radiological confirmation.

Subjects who discontinue all study medication for any reason should remain in the study for long-term follow up assessments unless they withdraw informed consent, die, or become lost to follow up. Long-term follow up evaluations will be performed accordingly as described in the protocol. In the event of study treatment discontinuation, the subject should be instructed to report to the site as early as possible after the decision to discontinue study treatment has been made. All End of Treatment procedures should be performed according to the protocol.

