6.1.6. Dose Adjustments/Modifications/Delays

No dose modifications are allowed for devimistat in this study.

The dose of Folinic Acid is not modified for any toxicity but is omitted if fluorouracil is omitted. Once a dose of any of the drugs comprising FFX is decreased, re-escalation of the dose is not permitted. Patients are taken off the study if they develop the same Grade 4 toxicity despite dose reduction. The dose adjustment scheme for FFX is dependent on the type of toxicities, as described below.

Hematologic Toxicity

Once hematologic toxicity is observed in a patient, do not retreat the patient with mFFX or FFX until the absolute neutrophil count is $\geq 1.5 \times 10^9/L$ and the platelet count is $\geq 75 \times 10^9/L$. The dose modification schemes for FFX related to hematologic toxicity are shown in Table 9.

Primary prophylaxis with myeloid growth factor will be at the discretion of the treating physician and as per the ASCO guidelines. If the patient is not being treated with myeloid growth factor the initial modification for neutropenia should be the addition of a myeloid growth factor. If the patient is already on a myeloid growth factor, then dose adjustments are as outlined in Table 9.

Table 9 Dose Modifications for Hematological Toxicities on Day 1 of a Cycle. Cycles are Every Two Weeks.

Day 1	Delay the Start of a Treatment Cycle*	Doses Reduction		
		Irinotecan	Oxaliplatin	Fluorouracil (5-FU)
ANC <1.5x10 ⁹ /L	Withhold treatment until granulocytes ≥1.5x10 ⁹ /L.	1 st occurrence: Continue same dose	1 st occurrence: Continue same dose	1 st occurrence: Delete bolus 5-FU
		2 nd occurrence: Reduce to 80% of starting dose	2 nd occurrence: Continue same dose	
		3 rd occurrence: Reduce to 50% of starting dose	3 rd occurrence: Reduce to 80% of starting dose	
		4 th occurrence: Discontinue irinotecan	4 th occurrence: Continue on 80% of starting dose	
Platelets <75x10 ⁹ /L	Withhold treatment until platelets ≥75x10 ⁹ /L.	1 st occurrence: No dose reduction	1 st occurrence: No dose reduction	1 st occurrence: Delete bolus 5-FU
		2 nd occurrence: Reduce to 80% of starting dose	2 nd occurrence: Reduce to 80% of starting dose	
		3 rd occurrence: Reduce to 50% of starting dose	3 rd occurrence: Discontinue oxaliplatin	
		4 th occurrence: Discontinue irinotecan	4 th occurrence: Discontinue oxaliplatin	

Table 10 Dose Adjustments According to Non-Hematological Toxicities (Excluding Alopecia, Nausea and Vomiting).

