8.4. Reporting Procedures

8.4.1. Adverse Event Reporting

At each visit the subject will be queried on changes in his/her condition. During the reporting period of the trial any untoward changes in the subject's condition will be recorded as AE, whether reported by the subject or observed by investigator.

Any treatment-emergent abnormal laboratory result which is clinically significant (defined as meeting one or more of the below must be documented on the CRF.

1. Accompanied by clinical symptoms
2. Leading to a change in study medication (e.g., dose modification, interruption or permanent discontinuation)
3. Requiring a change in concomitant therapy (e.g., addition of, interruption of, discontinuation of, or any other change in a concomitant medication, therapy or treatment)

It is the responsibility of the investigator to document all AEs that occur during the study. AEs should be reported on the appropriate page of the CRF. AEs should be reported for their actual grade and duration. The severity of the AE will be graded according to the NCI CTCAE Grading Scale (Current version).

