9.4.4. Safety Analyses

The assessment of safety will be based mainly on the frequency of adverse events based on the Common Terminology Criteria for Adverse Events (CTCAE version 4) grade. Adverse events will be coded according to MedDRA, current version. The safety outcomes will include the occurrence of at least one serious adverse event, of at least one grade 3/4 adverse event, and of at least one adverse event requiring the discontinuation of study treatment.

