7.1 Patient Disposition

Enrollment by country and center will be summarized for all randomized patients and also by treatment arm using the ITT population. The number of patients in each population will be tabulated by treatment arm and overall. Number screened and screen failed will be tabulated. Reason for screen failure will also be tabulated and listed.

The frequency of patients treated, of patients who discontinued the study treatment, and of patients who terminated the study will be displayed using the ITT population. The primary reason for discontinuation of the study treatment and terminating the study will be tabulated. The frequency of patients on treatment, who completed treatment, and their reason for discontinuation of treatment will be summarized by cycle.

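### SAP 6.3.3 plans no separate safety-population summary of AEs leading to permanent discontinuation, a safety outcome the protocol names

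*SAP*

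**What the plan says.** Protocol 9.4.4 bases the safety assessment mainly on adverse event frequency and names three patient-level outcomes: at least one serious event, at least one grade 3/4 event, and "at least one adverse event requiring the discontinuation of study treatment". The safety objective in protocol section 3 repeats the three.

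SAP 6.3.3 lists the adverse event tables for the safety population. The only one that concerns action on study drug is "Patients with at least one AE that led to a change in study medication (e.g., dose modification, interruption, or permanent discontinuation", shown by arm and overall. The same section keeps events still ongoing at data cut-off out of every listed table. It moves them to a separate table by SOC and CTCAE term.

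SAP 7.1, on disposition, adds "The primary reason for discontinuation of the study treatment and terminating the study will be tabulated" and "The frequency of patients on treatment, who completed treatment, and their reason for discontinuation of treatment will be summarized by cycle". That paragraph works in the ITT population.

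Protocol 8.3 requires the action taken with study drug to be documented for each event, and gives withdrawal and dose reduction as separate examples.

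**The concern.** The protocol fixes an outcome, and the SAP should say how it will be summarised. Here the outcome shares a line with two much milder consequences. Protocol 6.1.6 (Tables 9 and 10) provides for withholding a cycle, dropping bolus fluorouracil and reducing component doses in response to toxicity. Any one of these would place a patient in the combined line alongside someone who stopped treatment for good.

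The arms also start from different component doses: oxaliplatin 65 and irinotecan 140 mg/m² in Arm 1, against 85 and 180 mg/m² in Arm 2 (protocol 6.1.5, Tables 7 and 8). The frequency of modification could differ between arms for reasons that say little about how often patients stop. A combined count cannot tell the two apart.

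At stake is a clear, pre-specified answer on stopping for toxicity in an open-label comparison of two toxic regimens. If the split is left until after results are known, its definition becomes a post hoc choice.

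**Working it through.** The plan attaches no figure to this point, so the check matches each protocol outcome to the planned outputs.

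| Protocol outcome (sections 3 and 9.4.4) | Output in SAP 6.3.3 | Match |
|---|---|---|
| At least one SAE | Patients with an SAE, by SOC and CTCAE term | Direct |
| At least one grade 3/4 AE | Patients with an AE, by severity | Obtainable from the grades |
| At least one AE requiring discontinuation | Line combined with dose modification and interruption | No separate summary stated |

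**Possible origin of the line.** Protocol 8.4.1 has almost the same phrase, "Leading to a change in study medication (e.g., dose modification, interruption or permanent discontinuation". There it is one criterion for a clinically significant laboratory result, a different purpose from the safety outcome in 9.4.4. That the SAP line was taken from there is an inference.

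**Does SAP 7.1 fill the gap?** Protocol 5.3.1 requires the reason for discontinuation to be recorded, and its list, introduced by "Possible reasons for the discontinuation may include, but are not limited to, the following", includes adverse event. SAP section 5 makes display by arm the default for post-randomization tables. A by-arm count of patients whose primary reason was an adverse event can therefore be expected. It differs from the protocol outcome in four ways:

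1. *Population.* Disposition uses the ITT population, by allocated arm. SAP 5.2.3 assigns safety analyses to treated patients, by treatment received.
2. *Counting rule.* It records one primary reason per patient. The protocol counts every patient with at least one such event, whatever reason was entered as primary.
3. *Detail.* It gives no SOC or CTCAE term.
4. *Spread of reasons.* Besides adverse event, protocol 5.3.1 lists a delay of more than 3 weeks because of toxicity, unacceptable toxicity, and recurrent grade 4 events. If the case report form keeps these as separate entries, the adverse event row undercounts stops caused by toxicity. The documents do not show how the form handles them.

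**Ongoing events.** An unresolved event that caused a patient to stop would, under SAP 6.3.3, leave the combined line. It would appear only in the ongoing-events table, which is not broken down by action taken. Even the combined line would then be incomplete for this outcome.

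**Feasibility.** Protocol 8.3 distinguishes withdrawal from dose reduction, so the split by action can be made from data already collected. Whether action is recorded separately for each drug is not stated.

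**The case against.** A reader might infer that the discontinuation outcome will not be reported at all and that the tolerability question goes unanswered. The documents do not support that. SAP 7.1 plans a table of the primary reason for stopping, and a sizeable difference between arms in stopping for adverse events would be expected to show there. What survives is that this table is a proxy and not the outcome in protocol 9.4.4.

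A reader might also infer that the SAP commits to one merged percentage. It does not. The line names a table and lists actions as examples, with no layout; neighbouring lines are equally brief. The supportable statement is that no split is specified.

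A third inference is that separate tables for devimistat and for each FOLFIRINOX component are owed because "No dose modifications are allowed for devimistat in this study". The protocol outcome is discontinuation of study treatment, with no per-drug requirement. The rule on devimistat dosing creates no reporting duty, and per-drug action data are not shown to exist.

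Nor can the size of any masking be claimed. Tables 9 and 10 give rules for adjustment, not frequencies, and no expected rates appear anywhere.

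Two limits stand. Parts of the SAP after section 9, including the text of section 12 on changes from the protocol, are not in the copy available, so a further output or a declared change there cannot be excluded. Safety also lies outside the testing hierarchy (protocol 9.4.2, SAP 5.4), so no formal conclusion depends on this.

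**Conclusion.** The point holds as a gap in specification. One of the three patient-level safety outcomes named in the protocol has no separate safety-population summary in the available SAP 6.3.3. It appears only in a line shared with dose modification and interruption, and the disposition table in SAP 7.1 is a partial substitute. The OS, PFS, ORR and DOR analyses are unaffected, and no numerical effect can be given. The conclusion assumes that the unavailable SAP text contains no further adverse event output and no declared departure from protocol 9.4.4. It is worth correcting before the table layouts are fixed, because the outcome is named in the protocol and the correction is cheap.

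**What to change.** In SAP 6.3.3, replace the combined line with two summaries in the safety population, both derived from the action-taken field in protocol 8.3:

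- (a) patients with at least one AE leading to permanent discontinuation of study treatment, by arm and by SOC and CTCAE term;
- (b) patients with at least one AE leading to dose modification or interruption, by arm.

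Exempt table (a) from the rule that removes events ongoing at data cut-off, so that an unresolved event that caused a patient to stop is counted. State in table (a) whether stopping a single component counts as discontinuation of study treatment. Add a per-component split only if action taken is recorded for each drug.

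Keep the SAP 7.1 disposition table as it stands, since it answers a related but different question. The cost is a small amount of programming. No new data collection is needed for (a) and (b), and no efficacy analysis changes.

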2.3. Risk/Benefit Assessment

Please refer to the appendix III for study-specific assessment for details.

Primary Objective:

- To determine efficacy of devimistat plus mFFX compared to standard care FFX in terms of **Overall Survival (OS)**

Secondary Objectives:

- To determine efficacy of devimistat plus mFFX compared to standard care FFX in terms of **Progression-Free Survival (PFS)**.
- To determine efficacy of devimistat plus modified FOLFIRINOX (mFFX) compared to standard care FOLFIRINOX (FFX) in terms of **Objective Response Rate (ORR)**. ORR is defined as Complete Response (CR) plus Partial Response (PR).
- To evaluate **Duration of Response (DOR)**
- **Safety Analysis:** The assessment of safety will be based mainly on the frequency of adverse events based on the Common Terminology Criteria for Adverse Events (CTCAE version 4) grade. Adverse events will be coded according to MedDRA. The safety outcomes will include the occurrence of at least one serious adverse event, of at least one grade 3/4 adverse event, and of at least one adverse event requiring the discontinuation of study treatment. **QTc** intervals will be also evaluated as part of safety analysis.
- To assess **PK** of devimistat.
- To evaluate **Patient-Reported Outcomes (PRO)** for devimistat plus mFFX compared to standard care FFX.

Exploratory Objectives:

- To explore **biomarkers** using diagnostic biopsies and blood/plasma samples.
- To assess **PK/PD** of **dose/exposure-response** for devimistat on efficacy (e.g. PFS), safety (e.g. QTc) and exploratory biomarkers.

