8.3. Time Period and Frequency for Event Assessment and Follow-Up

The occurrence of an AE or SAE may come to the attention of study personnel during study visits and interviews of a study participant presenting for medical care, or upon review by a study monitor. All AEs including local and systemic reactions not meeting the criteria for SAEs will be captured in the CRF. Information to be collected includes event description, time of onset, clinician's assessment of severity, relationship to study product (assessed only by those with the training and authority to make a diagnosis), and time of resolution/stabilization of the event. All AEs occurring while on study must be documented appropriately regardless of relationship, action taken with study drug (drug withdrawn, dose reduced), other treatment for AE (drug therapy, other procedure) and outcome of AE. All AEs will be followed to adequate resolution (return to baseline).

Any medical condition that is present at the time that the participant is screened will be considered as baseline and not reported as an AE. However, if the study participant's condition deteriorates at any time during the study, it will be recorded as an AE. UPs will be recorded in the data collection system throughout the study.

Changes in the severity of an AE will be documented to allow an assessment of the duration of the event at each level of severity to be performed. AEs characterized as intermittent require documentation of onset and duration of each episode. Disease progression will not be considered as an AE/SAE.

The PI will record all reportable events with start dates occurring any time after informed

consent is obtained until 7 (for non-serious AEs) or 30 days (for SAEs) after the last dose of the study drug. At each study visit, the investigator will inquire about the occurrence of AE/SAEs since the last visit. Events will be followed for outcome information until resolution or stabilization.

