5.1 Milestones and Planned Analyses

5.1.1 Final Analysis

The final analysis will be done with 528 patients randomized about 33 months after starting accrual, when at least 335 OS events are available. If the trial reaches statistical significance for the primary endpoint, PFS and other secondary endpoints will be tested sequentially using a type-I error level of 0.025.

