5.2.3 Safety Population

The safety population consists of all randomized subjects who received at least one dose of study treatment, analyzed according to the treatment received. The safety population will be used for safety analyses.

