5.7 Missing Data

For the primary and key secondary efficacy analyses, imputation will be performed. Imputation rules for partial PFS dates are as follows:

- 1) If year is missing, no imputation should be done;
- 2) If only day is missing, then impute the day as the 15th of the month;
- 3) If both day and month are missing, then impute the day and month as 1st of July;
- 4) All imputed dates have to be prior to the dates of withdrawal of consent, lost to follow-up, and death.

Imputation rules for partial death dates are as follows:

- 1) When only date portion is missing and month and year are available, the death date will be imputed to the last day of that month.
- 2) When date and month portion is missing and year is available, the death date will be imputed to maximum of (30th June of year of death / last known alive date / last follow up date / maximum date from selected SDTM datasets / end of study date).

For determination of treatment emergent adverse events the following rules will be applied for all treated subjects in case of missing start date:

- If end date is before the date of first treatment administration, the start date will remain missing
- If start date is missing and end date is after or on the date of first treatment administration or the end date is missing, the start date will be imputed by the date of first treatment administration
- If start date is incomplete and end date is after or on the date of first treatment administration or the end date is missing, the start date will be imputed as follows: if the day is missing then the start date will be imputed with the first day of the month; if the day and month are missing then the start date will be imputed with minimum of (1 December of the year and the AE end date).

Confidential

6. Techniques for the Analyses

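### The SAP leaves every adverse event still ongoing at data cut-off out of all eight AE and SAE tables, so the protocol's occurrence outcomes are undercounted

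*SAP*

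**What the plan says.** SAP 6.3.3 lists eight summaries on the safety population:

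- all AEs, and patients with an AE, by SOC and CTCAE term
- patients with an AE by relatedness, and by severity
- all SAEs, and patients with an SAE, by SOC and term
- patients whose AE changed study medication, and patients whose AE changed concomitant therapy

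It then adds: "Adverse events that are still ongoing at the time of data cut-off should not be included in any of the tables described above". In their place, "a separate table should be presented containing all on-going AEs by SOC and CTCAE term, by treatment arm and overall".

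The denominator is set in SAP 5.2.3: "The safety population consists of all randomized subjects who received at least one dose of study treatment, analyzed according to the treatment received".

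Protocol 9.4.4 defines the safety outcomes as "the occurrence of at least one serious adverse event, of at least one grade 3/4 adverse event". It adds a third outcome, also given in the protocol's objectives (Section 3, printed after 2.3): "of at least one adverse event requiring the discontinuation of study treatment". None of the three depends on the event having resolved.

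**The concern.** An occurrence outcome asks whether a patient ever had the event. Under the SAP's rule, a patient whose only SAE is unresolved is counted as having had no SAE.

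Open events at cut-off are foreseeable. Protocol 8.3 states: "Events will be followed for outcome information until resolution or stabilization". Protocol 8.4.2 lets SAE follow-up end when the investigator judges the event chronic. Treatment continues until a removal criterion is met, so some patients may still be on drug at cut-off. In the phase I trial, sensory neuropathy occurred in 17 of 18 patients (94%) at the selected dose and developed late (Appendix III). The rule therefore removes persistent toxicity in particular.

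Safety against FFX is a secondary objective, and these eight tables are where AE and SAE incidence is reported. If the ongoing share differs between arms, the comparison is distorted as well. Unequal shares are plausible because the oxaliplatin and irinotecan doses differ by arm, but the direction cannot be derived from the documents.

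**Working it through.** The plan gives no figure for this point, so the check compares the texts and then illustrates the size.

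**1. Outcomes against tables**

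| Protocol outcome | SAP 6.3.3 table serving it | Under the exclusion? | Restored elsewhere in the text supplied? |
|---|---|---|---|
| Any SAE | Patients with an SAE | Yes | No |
| Any grade 3/4 AE | Patients with an AE by severity | Yes | No |
| Any AE requiring treatment to stop | Patients whose AE changed study medication (pools modification, interruption and discontinuation) | Yes | Partly: primary reason for stopping treatment (SAP 7.1) |

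Deaths are summarised separately in 6.3.3 and are not affected. SAP Section 5 promises listings only where noted, and 6.3.3 notes one for deaths only.

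**2. Undercount in one row.** Let p be the true share of patients with the outcome, and q the share of those patients whose qualifying events are all open. Then reported incidence = p(1 − q). Neither p nor q is in the documents. Assume p = 25% and q = 10% or 30%:

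- q = 10%: 0.25 × 0.90 = 22.5%. Patients missing per arm: 250 × 0.25 × 0.10 = 6.25, or 264 × 0.25 × 0.10 = 6.6.
- q = 30%: 0.25 × 0.70 = 17.5%. Patients missing per arm: 250 × 0.25 × 0.30 = 18.75, or 264 × 0.25 × 0.30 = 19.8.

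The arm sizes are half of 500 (protocol 9.5) and half of 528 (SAP 5.1.1). They count randomised patients, so the treated numbers can only be equal or smaller.

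**3. Can the ongoing table restore the count?** Let R be the patients in a main-table row and O the patients in the ongoing table. O carries no grade or seriousness, and the same patient may be in both, so the true count lies anywhere from R to R + O. As a hypothetical case, take R = 100 with grade 3/4 and O = 60 with an open event of any grade, in 250 patients. The true figure is then between 100/250 = 40% and 160/250 = 64%.

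**4. Which rows are exposed?** A patient drops out of a row only if all of that patient's qualifying events are open. Phase I recorded 118 grade 3 or higher toxicities in 20 patients, or 118/20 = 5.9 each. Assume each event is open independently with probability 0.3. The share of affected patients lost from an any-grade-3/4 row is then:

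- Poisson counts: (e^(5.9×0.3) − 1)/(e^5.9 − 1) = 4.871/364.0 = 1.3%
- Geometric counts, G(s) = 1/(1 + 5.9(1 − s)): (G(0.3) − G(0))/(1 − G(0)) = (0.1949 − 0.1449)/0.8551 = 5.9%
- Exactly one event per patient: 30%

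**5. Arm comparison.** With equal q, both arms shrink by the same factor. With a true 25% in each arm and q = 10% against 30%, the tables show 22.5% against 17.5%, a spurious 5-point gap. With a true 15% against 25% and q = 20% against 50%, they show 0.15 × 0.80 = 12.0% against 0.25 × 0.50 = 12.5%, which hides a 10-point gap. These q values are illustrations only.

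**6. A rough guide to q.** SAP 5.1.1 says: "The final analysis will be done with 528 patients randomized about 33 months after starting accrual, when at least 335 OS events are available". At 335 deaths, (500 − 335)/500 = 33.0% to (528 − 335)/528 = 36.6% of patients are not recorded as dead; this includes patients lost to follow-up. A q well above 30% is therefore unlikely unless events unresolved at death also count as ongoing. The SAP text supplied does not settle that.

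**The case against.** The strongest reply is that events are moved, not lost, and that the tables are descriptive. Parts of it stand:

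- If the all-AE table counts events, it and the ongoing table share a layout and can be summed by term and arm. This rescues event counts, but not the patient-level tables, nor the all-SAE table, because the ongoing table does not separate serious events.
- SAP 5.7 gives an imputed start date to an event described by "If start date is missing and end date is after or on the date of first treatment administration or the end date is missing". Such an event can be treatment-emergent and still be sent to the ongoing table. This is a tension only if a missing end date is read as ongoing, and not a contradiction.
- Every q above is assumed. The dilution model treats events as independent, although open status probably clusters within patients.
- No safety hypothesis test is planned, the data stay in the database, SAEs still reach the sponsor within 24 hours, and the DMC reviews accumulating safety data.
- SAP Sections 10 and 12 are not in the text supplied, nor are table shells. Whether the departure was declared cannot be judged.

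None of this returns an open SAE or grade 3/4 event to the patient-level counts that the protocol names. Descriptive tables are also the only form in which safety is compared.

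**Conclusion.** The concern holds. Followed literally, SAP 6.3.3 reports a different quantity from the one defined in protocol 9.4.4: patients with a *resolved* qualifying event, over all treated patients. A row is too low whenever some patient's qualifying events are all open, and the outputs described cannot recover the right count.

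The size depends on q, which the documents do not give. For q of 10% to 30%, a single-event row loses that same proportion of its affected patients. Any-AE and any-grade-3/4 rows lose much less, roughly 1% to 6% under the assumptions shown. Distortion between arms needs unequal q, and neither its size nor its direction can be derived. Deaths, the OS test and the tested hierarchy are untouched, and the discontinuation outcome is partly covered by SAP 7.1. The rule should be corrected before the tables are produced.

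**What to change.** Delete the exclusion sentence from SAP 6.3.3. In each of the eight tables, count every AE that otherwise qualifies (under the treatment-emergent rules of SAP 5.7 where they apply) with onset up to data cut-off, whether or not it has ended. The reported rate then equals the true rate for any q.

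Keep the ongoing-event table as a supplement, and define *ongoing* for it. The definition should cover events with an unknown end date, events judged stable or chronic, and events unresolved at death.

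The cost is SAP wording and table programming, with no new data. Reported AE and SAE rates will be somewhat less favourable. This change does not separate discontinuation from modification and interruption in the study-medication table; that would need its own row.
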